**Study Synopsis**

Title of clinical trial	Optimization of sampling for molecular microbial research on ocular surface samples and building a framework for comparing current sequencing results using different extraction protocols.
Protocol Short Title/Acronym	EPSO
Funding	LRD/ KU Leuven: EFW-FOPRD1-O2010 (Perdaens Eye Research Fonds) UZ Leuven: Fonds Academisch onderzoek S62672
Principal Investigator	[name]
Sponsor	University Hospitals Leuven [name]
Purpose of clinical trial	Optimization of ocular sampling for microbial research and to provide a framework for the interpretation of research results for ocular surface microbiome studies based on differences in DNA extraction procedures of complex microbial communities.
Trial Design	Exploratory study using biological samples
Summary of eligibility criteria	

• <math>\geq 18</math> years old

• Willing to undergo sampling of the conjunctiva

• Fluent in written and verbal Dutch

• Capable of giving informed consent

Study protocol EPSO v 7.0 dd 01.02.2021:

Optimization of sampling for molecular microbial research on ocular surface samples and building a framework for comparing current sequencing results using different extraction protocols.

Version and date of final protocol	v 7.0 dd 01.02.2021
------------------------------------	---------------------

## 1. Background, rationale and novelty

The human microbiome is the collective genomic information of the community of commensal, symbiotic and pathogenic microorganisms that share our body space. They play a role in metabolism, homeostasis and maturation of the immune system (1)

Since the publication of the Human Microbiome Project in 2008, a lot of research on the presence of a core microbiome on different body parts such as gut, skin and mouth has been executed. More and more evidence is emanating that a dysbiotic microbiome can induce a variety of autoimmune and inflammatory diseases. Especially the relationship between the intestinal microbiome and different inflammatory diseases has been widely investigated (2).

Since culture-based methods only reflect a subset of the microorganisms present in complex human associated microbial communities, it is necessary to additionally use culture independent methods to further investigate the presence of a “core” microbiome per microbial habitat (3). High-throughput sequencing, such as amplicon-based studies or metagenomic studies are the current way to go. Targeted amplicon studies, such as 16S rRNA amplicon sequencing, focus on marker genes and use these markers to reveal the composition and diversity of the microbiota. Part of the 16S rRNA gene is amplified by PCR with universal primers that recognize highly conserved regions of the gene. This region is then further sequenced. Metagenomic studies, as shotgun whole genome sequencing (WGS) use, instead of universal primers, random primers to sequence overlapping regions of the complete genome (4, 5)

Several studies have described the presence of a core ocular surface microbiome, but the difference in methods used makes them quite difficult to compare.

In terms of used swabs, some studies use sterile cotton swabs (6-11) others nylon flocked swabs (2). Also, the use of **anesthetics** is subject for discussion. Some researchers use anesthetics as this would improve the sampling on subjects (11, 12). However, since Shin et al. (9) published a significant higher alpha diversity when no anesthetic was used, most sampling was performed without anesthesia. The latter publication did however not provide any information on timing

Study protocol EPSO v 7.0 dd 01.02.2021:

Optimization of sampling for molecular microbial research on ocular surface samples and building a framework for comparing current sequencing results using different extraction protocols.

between application and sampling. Indeed, the described effect could also be due to the diluting effect of the drop itself. In any case, when using a topical anesthetic drop, the firmness of the sampling can be considered influenced. Possibly there is a vertical stratification with the presence of transient species in the more superficial layers and a more resident commensal microbiota in the deeper layers (7).

To compare the effect of anesthetic drops, we decided to sample volunteers undergoing general anesthesia for any type of surgery. The right and left eye of one person will be randomized for a drop of artificial tears (Thealoz duo®, Théa Pharma, Clermont – Ferrand, Cedex 2, France) or a drop of topical anesthesia (Minims® Oxybuprocaine Hydrochloride 0.4%, Bausch and Lomb, Aubenas, Frankrijk). One drop of Thealoz duo® has the same weight as one drop of Minims® Oxybuprocaine Hydrochloride 0.4%, (both 0,02 g), this makes the diluting effect comparable. The executer will be blinded. The rationale for general anesthesia is that the sampling pressure/depth will be similar with or without topical anesthesia since the executer won't be influenced by the patients reaction. By comparing both eyes of one person, the immunological and genetic background will be the same. Moreover, Shalabi et al. showed a high level of concordance in microbiome composition in the same-person eyes (13). The effect of environmental factors, such as the effect of repeatedly sleeping on one side, will be minimalized by randomization. To have the possibility to take the most obvious confounding factors in account, subjects will be asked to fill in a small questionnaire (*see addendum A*).

In gut and oral microbiome research, it is currently acknowledged that the used **DNA extraction method** plays a crucial role in the recovery of microbial taxa (14-16). However, researchers focusing on less studied human microbial niches, like the ocular surface, seem not yet to be aware of the impact thereof. The ideal extraction protocol should reflect the microbial richness and diversity present on the eye as adequate as possible since the DNA extraction method affects the observed species diversity downstream. We aim at comprehensible integration of the results from the scarce microbiota studies published in this field, by

**Legend**  
ind: individual, RE: right eye, LE: left eye  
**Colour code**  
DNeasy PowerSoil® Kit  
DNeasy Blood & Tissue® Kit  
Nucleospin® tissue  
QIAamp DNA microbiome® kit (with human depletion)  
RNeasy PowerMicrobiome® Kit  
FastDNA™ Spin Kit for Soil  
QIAamp DNA microbiome® kit (without human depletion)

*Figure 1*

Although the immunological and genetic background in one person are the same and [Shalabi et al.](#) showed a high level of concordance in microbiome composition in the same-person eyes (13), the environmental factors may differ between eyes. First of all, patients are known unilateral eye rubbers, with sometimes clinical consequences such as keratoconus (17). Secondly, repeatedly sleeping on one side can have an effect on the ocular surface microbiome as well due to rubbing of the eyelid against the pillow and nocturnal eyelid eversion (18). To further clarify the effect of environmental factors on both eyes within one individual, the 7 volunteers mentioned before will be asked to fill in a questionnaire (*cfr. addendum A*).

The **ambition** of this study is to make our research done in this area more robust since it will determine our method used in each future project.

## 2. Trial objectives and design

We aim at clarifying 1) if the reported effects of the use of anaesthetic drops (9) are due to dilution of samples or not, 2) how different DNA extraction protocols distort our view on ocular

Study protocol EPSO v 7.0 dd 01.02.2021:

Optimization of sampling for molecular microbial research on ocular surface samples and building a framework for comparing current sequencing results using different extraction protocols.

surface microbiota composition and 3) the degree of similarity between left and right eye in the same person.

## 2.1 Preparation, organization and management of this exploratory study

### **Part 1: Effect of the use of anaesthetic drops on ocular microbial composition using 16S rRNA sequencing.**

Study cohort:

**Thirty volunteers** undergoing general anaesthesia for any type of surgery will be informed about the study upon their consultation at the Ophthalmology Department of the University Hospitals Leuven, Belgium. In case a candidate is interested in participating, he/she will be informed about the study goals and protocols by *[name]* or the responsible clinical research coordinator *[name]* during a personal conversation. Each volunteer will receive an information letter to take home.

Study procedure:

After signing the informed consent, each patient will be asked to fill in a questionnaire (*cfr. addendum A*).

All participants will undergo conjunctival sampling of both eyes **under general anaesthesia**. The research coordinator or operating room nurse will apply one drop of preservative free artificial tears to one eye Thealoz duo®, Théa Pharma, Clermont – Ferrand, Cedex 2, France) and one drop of preservative free anaesthetics (Minims® Oxybuprocaine Hydrochloride 0.4%, Bausch and Lomb, Aubenas, Frankrijk) to the other eye. A timed 5 minutes will be in between application of the drop and the sampling. The sampling will be blinded for the executer and will be performed by myself, [name], and/or residents and/ or medical students after proper training of correct sampling. Each eye will be sampled with a single, sterile, nylon, flocked swab (FLOQSwabs®; Copan, Brescia, Italy). The

Study protocol EPSO v 7.0 dd 01.02.2021:

Optimization of sampling for molecular microbial research on ocular surface samples and building a framework for comparing current sequencing results using different extraction protocols.

sampling will be done from the nasal to temporal inferior conjunctival sac, the swab will be swirled in the opposite direction of the sampling itself. The swabs will be placed in a microcentrifuge tube and immediately frozen at  $-20^{\circ}\text{C}$  for a maximum period of 2 weeks, after which they will be transferred to a  $-80^{\circ}\text{C}$  freezer until further processing. DNeasy PowerSoil® Kit will be used for DNA extraction. This extraction protocol is chosen based on its frequency used in ocular surface microbiome research. The extracted DNA will be analysed using the V4 region of the 16S rRNA gene. All steps in between sample taking and sequencing will be executed at the REGA institute for medical research or department of Biochemistry and Microbiology of the University of Gent. The sequencing itself will be done at a sequencing facility.

**Part 2: Clarification on how different DNA extraction protocols distort our view on ocular surface microbiota composition.**

Study cohort:

*Seven volunteers* will be recruited using a poster at the Ophthalmology Department of the University Hospitals Leuven, Belgium and at the faculty of medicine, Catholic University Leuven, Belgium (*cf. addendum B*). In case a candidate is interested in participating, he/she will be informed about the study goals and protocols by *[name]* or the responsible clinical research coordinator *[name]* during a personal conversation. Each volunteer will receive an information letter to take home.

Study procedure:

After signing the informed consent, all eligible participants will be asked to fill in a small questionnaire (*cf. addendum A*), after which they will undergo conjunctival sampling on 7 different points in time (*figure 1*). Based on the results of the first part of the study we will not use anaesthetic drops.

There is no need for general anaesthesia. The sampling will be performed by myself, [name], and/or residents and/ or medical students after proper training of correct sampling. Each eye will be sampled with a single, sterile, nylon, flocked swab (FLOQSwabs®; Copan, Brescia, Italy). The sampling will be done from the nasal to temporal inferior conjunctival sac,

Study protocol EPSO v 7.0 dd 01.02.2021:

Optimization of sampling for molecular microbial research on ocular surface samples and building a framework for comparing current sequencing results using different extraction protocols.

the swab will be swirled in the opposite direction of the sampling itself. The swabs will be placed in a microcentrifuge tube and immediately frozen at  $-20^{\circ}\text{C}$  for a maximum of 2 weeks, after which they will be transferred to a  $-80^{\circ}\text{C}$  freezer until processing. Six extraction protocols will be compared, of which one with and without human depletion. The extracted DNA will be analysed using the V4 region of the 16S rRNA gene. All steps in between sample taking and sequencing will be executed at the REGA institute for medical research or department of Biochemistry and Microbiology of the University of Gent. The sequencing itself will be done at a sequencing facility.

**Part 3: What is the degree of similarity between left and right eye in the same person.**

Study cohort and procedure:

Part 3 is based on the questionnaire and sampling results of the *seven subjects* used in *part 2*.

### **3. Selection and withdrawal of subjects**

#### **3.1 Inclusion criteria**

**Part 1: Effect of the use of anaesthetic drops on ocular microbial composition using 16S rRNA sequencing.**

Subject has to be older than 18 years old

Subject undergoes general anaesthesia for whatever reason

The subject is willing to undergo sampling of the conjunctiva of both eyes

The subject is fluent in written and verbal Dutch

The subject is capable of giving informed consent

**Part 2: Clarification on how different DNA extraction protocols distort our view on ocular surface microbiota composition.**

Study protocol EPSO v 7.0 dd 01.02.2021:

Optimization of sampling for molecular microbial research on ocular surface samples and building a framework for comparing current sequencing results using different extraction protocols.

Subject has to be older than 18 years old

The subject is willing to undergo sampling of the conjunctiva of both eyes on 7 different time points

The subject is fluent in written and verbal Dutch

The subject is capable of giving informed consent

### 3.2 Exclusion criteria

- Allergy to Oxybuprocainehydrochloride
- Ocular surface disease
- Medication usage in one eye only

### 3.3 Expected duration of trial

Inclusion of subjects is planned between August the 15th 2019 and the end of December 2020.

## 4. Trial procedures

### 4.1 Summary of visits

**Part 1: Effect of the use of anaesthetic drops on ocular microbial composition using 16S rRNA sequencing.**

The conjunctival samples will take place at time of the planned general anesthesia. No additional visits are necessary.

**Part 2: Clarification on how different DNA extraction protocols distort our view on ocular surface microbiota composition.**

The conjunctival samples will take place at the Ophthalmology Department of the University Hospitals Leuven, Belgium on 7 different points in time. Sampling will take less than 5 minutes. To compensate for travel expenses and time invested, each participant will receive at

Study protocol EPSO v 7.0 dd 01.02.2021:

Optimization of sampling for molecular microbial research on ocular surface samples and building a framework for comparing current sequencing results using different extraction protocols.

the end of their participation a voucher of 50 euros.

## **4.2 Supervision and responsibilities**

The study will be performed under the supervision of [name]. The subjects will be recruited at the Ophthalmology Department of the University Hospitals Leuven, Belgium and at the faculty of medicine, Catholic University Leuven, Belgium. The sampling will be performed by myself, [name], and residents and/ or medical students. Each study subject will sign an informed consent. The participating investigators will perform their part of the study fully in accordance with the terms of the Protocol, the applicable national and international laws (amongst others: the European General Data Protection Regulation of May 25, 2018) and apply and adhere to regulations and rules as, amongst others, the Declaration of Helsinki (2008) and ICH GCP Guidelines.

### *4.2.1 Insurance*

In accordance with the Belgian Law relating to experiments on human persons dated May 7, 2004, UZ/KU Leuven shall assume, even without fault, the responsibility of any damages incurred by a Study Patient from the UZ/KU Leuven site and linked directly or indirectly to the participation to the Study, and shall provide compensation therefore through their insurance (Amlin Corporate Insurance, polisnr. 299.053.700, Vanbreda Risk & Benefits, [name]).

### *4.2.2 Informed consent*

The Participating Site acknowledges that the Study can and will be conducted only on the basis of prior informed consent by the Subjects, or their legal representatives, to participate in the Study. The Participating Site shall obtain a signed informed consent form (ICF) for all patients prior to their enrollment and participation in the Study in compliance with all applicable laws,

Study protocol EPSO v 7.0 dd 01.02.2021:

Optimization of sampling for molecular microbial research on ocular surface samples and building a framework for comparing current sequencing results using different extraction protocols.

regulations and the approval of the local Ethics Committee, if required. The Participating Site shall retain such ICFs in accordance with the requirements of all applicable regulatory agencies and laws.

## 5. Assessment of efficacy

Not applicable

## 6. Assessment of safety

When sampling is not performed under general anesthesia, a slight discomfort can be perceived.

When topical anaesthetics are being used, a transient stinging and blurring of the vision after instillation can occur. When used in larger amounts, epitheliopathy of the cornea can be noticed. This is only rare in the case of one drop. Systemic absorption will be reduced by asking the patient to gently close the lids and to press on the medial canthus for a minute following the instillation of the drops. There are no known interactions with other medical products. It will not be used during pregnancy or lactation, nor will it be used in patients with a known hypersensitivity to the product.

After sampling the conjunctiva, a minor bleeding can occur in the conjunctival sac which can induce a feeling of bruising of the tissue. Scarring due to the intervention is extremely rare.

## 7. Statistics

### 7.1 Sample size

Since this is an **exploratory study**, we are not able to perform proper sample sizing.

For the first part, we aim at sampling 30 patients (60 samples) taking into account a maximal loss of 10 samples due to processing issues. Taking this loss into account, we will be able to

Study protocol EPSO v 7.0 dd 01.02.2021:

Optimization of sampling for molecular microbial research on ocular surface samples and building a framework for comparing current sequencing results using different extraction protocols.

[figure not shown]
process 50 samples to elucidate if the use of anesthetic drops has an effect on the sequencing results.

For the second part, we wish to sample 7 volunteers so we can compare 7 extraction protocols on different subjects on non-consecutive days. Each protocol will be tested on a sample from a different individual on a different day (*figure 1*) to minimize possible confounding factors. In gut and oral microbiome research, samples are homogenized to make comparing of different extraction protocols possible. In ocular surface samples, the retrieved sample is too small for homogenization.

## 7.2 Randomization

A 30-patient **randomization list** will be generated by our clinical research coordinator using <https://www.randomizer.org>, where “1” will be a drop of preservative free anaesthetics in the right eye and “2” a drop of preservative free anaesthetics in the left eye.

By using this software, we are able to automate the randomization, this to reduce bias due to manual randomization. When analysing our results, we will search for other biases due to randomisation, which we will be taken into account.

The screenshot shows the Research Randomizer website interface. At the top, there is a navigation bar with the logo and the text "RESEARCH RANDOMIZER" on the left, and "RANDOMIZE TUTORIAL LINKS ABOUT" on the right. The main content area has a teal background and contains three input fields with labels and help text:

- How many sets of numbers do you want to generate?** Input field contains "30".  
▼ Help  
In some cases, you may wish to generate more than one set of numbers at a time (e.g., when randomly assigning people to experimental conditions in a "blocked" research design). If you wish to generate multiple sets of random numbers, simply enter the number of sets you want, and Research Randomizer will display all sets in the results.
- How many numbers per set?** Input field contains "1".  
▼ Help  
Specify how many numbers you want Research Randomizer to generate in each set. For example, a request for 5 numbers might yield the following set of random numbers: 2, 17, 23, 42, 50.
- Number range (e.g., 1-50)** Input field contains "1" and "2" on separate lines.

Study protocol EPSO v 7.0 dd 01.02.2021:

Optimization of sampling for molecular microbial research on ocular surface samples and building a framework for comparing current sequencing results using different extraction protocols.

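### The Part 1 list is 30 unrestricted draws, so the anaesthetic drop will usually be unevenly split between right and left eyes; a balanced list or a named side term would be a small, nearly free improvement

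*Combined protocol and SAP*

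**What the plan says.** Part 1 compares two drops within each person: one eye receives the topical anaesthetic and the other artificial tears. Section 7.2 (Randomization) says that a 30-patient list "will be generated by our clinical research coordinator using" a public website. Code 1 "will be a drop of preservative free anaesthetics in the right eye and" code 2 means the left eye. The screenshot in that section gives the settings. The field "How many sets of numbers do you want to generate" holds 30, the field for numbers per set holds 1, and the range is 1 to 2. No block, pairing or 15:15 rule is stated there or elsewhere.

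Section 1 (Background, rationale and novelty) states what the randomisation is meant to achieve: "The effect of environmental factors, such as the effect of repeatedly sleeping on one side, will be minimalized by randomization".

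Two other provisions bear on the point. Section 7.2 promises to look for other biases arising from randomisation and to take them into account, and Section 1 plans a questionnaire on the most obvious confounders. Neither names eye side. Section 7.3 (Analysis) lists diversity indices, distances and a permutational analysis of variance, without a term for side.

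On numbers, Section 7.1 (Sample size) says "we aim at sampling 30 patients (60 samples) taking into account a maximal loss of 10 samples due to processing issues".

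**The concern.** With one number per set, each set is a separate draw, so nothing ties one patient's code to another's. The list behaves like 30 coin flips, and at this size coin flips often come out uneven.

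Side matters because the Part 1 contrast is always one eye against the other. If right and left eyes differ on average across the cohort, and the anaesthetic went to the right eye more often, part of that difference will look like an effect of the drop. The protocol cannot assume that there is no such difference. The discussion under Figure 1 says that environmental factors may differ between eyes, and Section 2 makes left-right similarity the third objective. Side is known before allocation and takes two values, so it is the easiest nuisance factor to balance exactly.

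**Working it through.** **Inputs.** From Section 7.2: 30 sets, 1 number per set, range 1 to 2. From Section 7.1: 30 patients, 60 samples, up to 10 lost. Assumption: each draw is 1 or 2 with probability 1/2.

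**The plan's own figures.** List length is 30 × 1 = 30, as stated. Samples are 30 × 2 = 60, and 60 − 10 = 50, as stated. The documents give no target for right-left balance, so there is no figure of that kind to reproduce.

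**Chance of imbalance.** Let X be the number of patients with the anaesthetic in the right eye, X ~ Binomial(30, 0.5).

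P(15:15) = C(30,15)/2^30 = 155,117,520 / 1,073,741,824 = 0.144.

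| Split, either direction | Probability |
|---|---|
| Not exactly 15:15 | 0.856 |
| 17:13 or worse | 0.585 |
| 18:12 or worse | 0.362 |
| 20:10 or worse | 0.099 |
| 21:9 or worse | 0.043 |

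The expected absolute difference between the two counts is 4.3 patients. About 64% of lists (1 − 0.362) are 17:13 or closer.

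**What an imbalance does without a side term.** Write the within-person difference (anaesthetic eye minus tears eye) as D = δ + s·σ + error. Here δ is the drop effect, σ is the cohort-wide right-minus-left difference, and s is +1 if the anaesthetic went to the right eye and −1 if to the left. With n1 patients at +1 and n2 at −1, the mean of D has expectation δ + σ(n1 − n2)/30. The weight on σ is:

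- 15:15: 0
- 17:13: 4/30 = 0.13
- 18:12: 6/30 = 0.20
- 20:10: 10/30 = 0.33

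The sign of n1 − n2 is as likely to be positive as negative, so the weight averages zero over all possible lists. The contribution is a chance error in the one list used, not a bias of the method.

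**What a side term costs.** With side in the model, δ is estimated as the average of the two group means of D. Relative to 15:15, its variance is 30²/(4·n1·n2):

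- 18:12: 900/864 = 1.042
- 20:10: 900/800 = 1.125
- average over all lists (leaving out the two one-sided lists, whose combined probability is negligible): 1.037

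**What sample losses do to an exact balance.** Suppose the 10 lost samples fall at random in 10 different patients. Then 20 complete pairs remain. Starting from 15:15, the chance that they are exactly 10:10 is C(15,10)²/C(30,20) = 3,003²/30,045,015 = 0.30. A balanced list therefore need not give balanced analysed pairs.

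**The case against.** The case for leaving the plan alone is substantial.

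- **Simple randomisation is valid.** Every patient receives both drops, so the comparison is 30 against 30 eyes before losses whatever the list. The protocol promises no 15:15 split and calls itself exploratory. All of this stands. A reader might infer that the Part 1 comparison is biased or that the plan contradicts itself, and the documents support neither reading.
- **A 15:15 list does not address the factors the protocol names.** Sleeping side and unilateral eye rubbing fall on the right in some people and on the left in others. Balancing right against left cancels only a difference common to the cohort. The documents give no evidence of one, and they cite a study reporting high concordance between the two eyes of a person. This also stands: a balanced list should not be presented as controlling sleeping side.
- **The size is small.** Exact equality is a strict yardstick, and 18:12 costs only 4.2% in variance once side is modelled. The weights above multiply an unknown that may be zero. They apply to a mean difference, such as one in a diversity index, and do not carry over directly to Bray-Curtis, Jaccard or the permutational analysis. Agreed.
- **The change may come too late.** Section 3.3 planned inclusion to the end of December 2020, this version is dated 01.02.2021, and Section 2.1 (Part 2) refers to Part 1 results as the reason for not using anaesthetic drops. This suggests, without proving it, that the list has been used. A reader might infer that the remedy is simply to regenerate it, but that may no longer be possible.
- **The protocol already provides for biases and confounders.** The search for biases and the questionnaire are relevant, but they name no variable, model or rule. An adjustment chosen after seeing the data is weaker than a prespecified one.

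What remains is that nothing in the documents balances or adjusts for eye side, and that either step costs almost nothing.

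**Conclusion.** The point holds as a free improvement of small size. Taken as stated, the settings leave the anaesthetic drop unevenly split over right and left eyes in 86% of lists, and at 18:12 or worse in 36%. In an analysis that ignores side, a fifth of any cohort-wide right-left difference would enter the estimated drop effect at 18:12 and a third at 20:10. Adjusting for side removes this for an average variance cost of about 4%.

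The conclusion rests on three assumptions: draws with equal probability, a paired comparison of means, and a right-left difference shared by the cohort. If there is no such difference, nothing leaks into the drop effect.

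It would be tempting to say that a balanced list removes the problem altogether. It does not. Person-specific asymmetry remains, losses of up to 10 samples can undo the balance, and with a real side difference but no side term the residual variance of the paired comparison stays inflated even at 15:15.

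**What to change.** **If allocation is still open:** replace the list with a balanced one. One random permutation of the numbers 1 to 30 will do, with 1 to 15 meaning anaesthetic in the right eye and 16 to 30 in the left. Numbers must be unique within the set. The screenshot text does not show that option, so confirm it on the website or make the permutation in R, which Section 7.3 already uses. A single permutation is preferable to blocks of two, where the second allocation follows from the first. Keep the list from the person taking the samples, who is to be blinded.

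**In any case, and as the only remedy if the list has been used:** name eye side in Section 7.3 as a prespecified term in the paired Part 1 analysis, and report the achieved right:left split among the pairs analysed.

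**Cost:** different settings when the list is made, one sentence in Section 7.3 and one line in the report. No extra patients or samples are needed. The side term costs about 4% in variance on average with the present kind of list, and essentially nothing when the analysed pairs are balanced.
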